3.0 Inclusion and Exclusion Criteria

3.1 Screening for eligibility for study

Emergency Department Providers. The research study will be described to providers by the emergency department leadership and study leadership, both via email and at in-person business meetings. All ED providers

EHR-Based Medication Complete Communication (EMC²) Strategy to Promote Safe Opioid Use: A Physician Randomized Trial

(attending MD, resident MD, NP, PA) with the exception of study investigators will be eligible. Providers will be asked to complete a written consent form if they choose to be involved in the study.

Patients. During the patient recruitment period, the RA will make frequent rounds through the ED and ask physicians to identify potentially eligible patients who will be discharged home on opioid pain relievers. The RA also will carry a pager so that physicians can notify the RA if they have an eligible patient. This method of patient identification has a well-established track record within our ED for maximizing enrollment while minimizing RA downtime. If the patient is interested in participating or learning more about the study, the RA will obtain verbal permission to ask the patient a brief series of questions to determine eligibility (see criteria below). If the patient is eligible for the study, the RA will proceed with obtaining written informed consent.

Follow-up Providers. Certain providers will interact with consented patients after the intervention takes place (e.g. Primary care physicians (PCP) and outpatient pharmacists). These providers will have no required role in carrying out the intervention (which is carried out by the EHR enhancements). These providers will be identified by chart review (PCP) and pill bottle review (pharmacists) at the time of patient follow-up. <30% of ED patients have on-staff PCP and there is no way to predict where the patients will fill their prescriptions (e.g., on-site Walgreens or another pharmacy). After identifying these providers at the time of follow-up, we will contact them via email or mail to participate in a survey. Both types of surveys will be offered to accommodate providers' busy schedules and because the pharmacists are located at diverse locations across the city of Chicago. The survey will assess the implementation of the EHR interventions and the providers' reactions to receiving additional information about their patients who were prescribed opioids in the ED.

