8.0 Study Endpoints

8.1 Covariates. Baseline assessment will include a sociodemographic and health questionnaire and questions about previous use of opioids. A literacy assessment using the Newest Vital Sign (NVS) will be performed.

Primary Endpoint. Demonstrated understanding of how to properly dose the opioid medication as measured by participants' ability to correctly dose their prescription regimen using a demonstrated dosing exercise previously used in studies by both Drs. [name] and [name]. Primary endpoint will be assessed at the 7-14 day phone interview.

Secondary Endpoint. Actual use of the opioid medication as measured through the review of the medication diary, participant report of refills and new opioid prescriptions received patient opinion of the intervention as measured by both closed and open-ended questions at the time of follow-up phone interview; patient risky-behaviors while on opioids, as measured by patient self-report. Other aspects of safe use related to *risk awareness* will be assessed using a questionnaire, as will beliefs about medication use. The questionnaire will assess topics including safe storage of opioids, sharing of opioids, disposal on completion of the prescription, and questions related to possible dangerous behaviors. Secondary endpoints will be assessed with phone interviews .

Tertiary Endpoints. The identification of medication names, dosage, risks, warnings, and benefits will be assessed through a structured questionnaire that has been developed and used extensively by [name] and colleagues in multiple studies and current NIH-funded grants. The self-report of provider counseling will also be measured. Tertiary endpoint assessments will be assessed via phone interviews.

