The initial study visit (baseline) will be conducted at the time of patient enrollment. Following this baseline interview, RAs will conduct three telephone interviews (at 2-4 days post-baseline, 7-14 days post-baseline and at one month post-baseline). The first two assessments (at enrollment and 2-4day follow-up call) have been included to closely track patient recall of counseling and knowledge, while the latter two assessments (7-14 day follow-up call and 1 month follow-up call) are included to assess decay of knowledge, safe use, storage of medications and demonstrated dosing. The final call (one month post-baseline) will assess disposal of

EHR-Based Medication Complete Communication (EMC²) Strategy to Promote Safe Opioid Use: A Physician Randomized Trial

medications and determine if patients have received additional opioid pain relievers from other providers.

Baseline Interview. At the time of enrollment, the RA will ask the participant to indicate the best days and times to call within a 2-4 day range. A \$5 Gift card given to the participant for completion of enrollment tasks.

First Study (2-4 Day) Phone Call. The study phone call will be conducted at a time of convenience for the patient, however still within a 2-4 day range post-baseline. Additionally during this phone call, the RA will either confirm or schedule the 7-14 day follow-up call. A \$10 Gift card will be mailed to the participant for completion of first phone call.

Second Study (7-14 Day) Phone Call. The second phone call will be conducted at a time of convenience for the patient, however still within 7-14 day range post-baseline. Patients will be compensated for their time to complete the call with a \$20 gift card which will be mailed to the participant upon completing the call. Patients will also be asked to mail back their de-identified medication diary using the prepaid envelope provided at baseline.

Third/Final Study (1 Month) Phone Call. The final study phone call will be conducted at a time of convenience for the patient, however still within 1-month post-baseline. (See Attached Interview script)

Intervention Patients with physicians randomized to the EMC² arm will receive the 5-part EMC2 intervention.

[figure not shown]

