[5] Finally, there will be a notification to the primary care physician (PCP) if the patient has a PCP in the Northwestern system. This notification was initially conceptualized as being automated when the inpatient and outpatient Cerner systems were compatible. Since the switch of the outpatient Northwestern Medicine offices to the EPIC EHR, this automated function is not longer available. Therefore, the RAs enrolling the subjects will note if the patient has a Northwestern Medicine physician. If the patient enrolled for follow-up has a physician in the system, the RA will manually log-in to the outpatient EPIC interface (with write functionality) and send the PCP an inbox message with the following sample text: "Your patient NAME, DOB was seen in the Northwestern Emergency Department on MONTH DATE, 20XX. They received a prescription for Hydrocodone-Acetaminophen (DOSE, TIMING, NUMBER OF TABS). When you see this patient for a follow-up appointment, please consider counseling them about the safe use of this medication. For additional information about your patient's visit to the Emergency Department, you may access the Emergency Department Note and Depart Summary. The Depart Summary will also contain a copy of the information sheet that your patient received about their new prescription pain medication."

EHR-Based Medication Complete Communication (EMC²) Strategy to Promote Safe Opioid Use: A Physician Randomized Trial

[Note: Neither the Pharmacist nor the PCP receiving the messages to “consider counseling the patient” are required to take any action as part of the intervention. The study is designed with the ED as point of care and we will be assessing implementation to gauge the response to these messages among those PCPs and pharmacist who received them; however, these providers are not required to do anything as part of the study or intervention.]

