AIM 2 Analysis Plan. Following completion of enrollment, we will determine the extent to which the interventions were implemented as planned (a process evaluation) in the two intervention arms. In the EMC² and EMC² + SMS text reminder arms, we will collect EHR data on prescriptions and discharge summaries to assess if patients actually received the new prescriptions with the UMS (Take-Wait-Stop) sig, and review pill bottle information during the 7-14 day phone call to determine if the sigs were translated accordingly onto patients' drug labels. For the EMC² + SMS text reminder arm, we will ask patients at all follow-up intervals if they received the text messages. For those electing to turn off the service, we will qualitatively explore and code reasons why.

Usability of the EHR interventions will be assessed among the ED physicians and follow-up providers (PCPs and pharmacists) via survey.

AIM 3 Analysis Plan. We will directly measure and assess the provider perspective costs of running the two EMC² interventions. Specifically, we will estimate the incremental cost of the interventions relative to usual care from the perspective of the ED implementing these systems. The primary costs of running the EMC² intervention involve the limited expenses around printing (printer ink, paper, staff time). However, we will include estimates for minimal programming maintenance and will test the sensitivity of results to changes in the maintenance requirements in terms of programmer hours. We also will separately track development costs for software and other programming requirements based on programmer hours. The greater cost, in terms of running the program, will be that for the SMS text services, which will include the nominal monthly cost as well as staff time to schedule the SMS text reminders after the initial ED visits. For study purposes, the RA will do this task; however, we will have record on a daily basis in a study database (Microsoft Office Access, Microsoft Corp.) the number of minutes spent programming the SMS text reminders. This record will allow us to estimate the direct staff costs of this component by combining time with wage estimates. We will test the sensitivity of costs to different assumptions about the potential use of variable staff (nurse, clerk, medical assistant) using different salaries but assuming the same proficiency in terms of time required. Further we will assess the sensitivity of the

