20.0 Resources Available

20.1 The research team is comprised of has 5 PhD level researchers, 3 Physician-researchers (all of whom hold research masters degrees), a research-pharmacist, and a group of research assistants and statistical analysts (who have 2-10 years of experience working on similar projects). We have significant experience in recruiting patients from the emergency department, conducting studies related to medications (including the medication being studied), consenting patients to follow-up, and conducting multi-part follow-up with both in-person and telephone interviews. Additionally, the team has experience in managing data in accordance with the best-practices of the IRB to protect patients' confidentiality.

20.2 Initial estimates suggest that approximately 9,000 subjects will be potentially eligible for follow-up annually (representing 16% of discharged patients from the ED).

The PI has 30% protected time for this study throughout the study duration and full support of the Department of Emergency Medicine. The Co-Is have ample time supported to assist in weekly meetings, data analysis, DSMB review, and other study operational tasks. The three physician-researchers will be available at all hours for the RAs to contact if there are any concerns related to the safety protocol (see attached).

EHR-Based Medication Complete Communication (EMC²) Strategy to Promote Safe Opioid Use: A Physician Randomized Trial

The study team will have 2 full-time RAs dedicated to enrolling and completing follow-up on the study with support from a team of other RAs to cover evening and weekend hours.

Facilities: The patients will be approached and consented for participation while in the Emergency Department. Follow-up calls by the RAs will occur at a time of convenience for the patient and the RAs have access to closed offices wherein to conduct the calls and record data.

All persons assisting in the project will be adequately informed about the research protocol, the research procedures, and their duties and functions. We will ensure this by conducting weekly research meetings (already in-place) and by reviewing key concepts and conducting practice sessions for the consent process and interviews.

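### No masking of the outcome assessor is described, and the research-assistant role that delivers arm-specific components also makes the 7-14 day call for the primary endpoint

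*Protocol*

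**What the plan says.** Protocol 20.2 provides "2 full-time RAs dedicated to enrolling and completing follow-up on the study with support from a team of other RAs"; the sentence goes on to say that the other RAs are there for evenings and weekends. The tasks of the RA role are spread over the protocol:

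- **Enrolment** (3.1, 22.3): RAs find patients by asking the treating physicians, then screen and consent them.
- **PCP message**, component 5 of EMC² (9.2): if the enrolled patient has a physician in the health system, "the RA will manually log-in to the outpatient EPIC interface (with write functionality) and send the PCP an inbox message". Section 3.1 states that "<30% of ED patients have on-staff PCP".
- **Texts**, EMC²+SMS arm only (11.1, Aim 3): running costs include "staff time to schedule the SMS text reminders after the initial ED visits. For study purposes, the RA will do this task".
- **Follow-up** (9.2): "RAs will conduct three telephone interviews".
- **Primary endpoint** (8.1), a demonstrated dosing exercise: "Primary endpoint will be assessed at the 7-14 day phone interview".

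The Aim 2 plan in 11.1 adds arm-specific content to the calls. The bottle label is reviewed in the two intervention arms during the 7-14 day call, and for the SMS arm "we will ask patients at all follow-up intervals if they received the text messages".

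The only blinding statement in either document concerns the person who randomises the providers, whose identities are revealed afterwards (9.2). The paragraph in 11.1 on minimising bias covers the unit of randomisation and the spill-over to patients who are not enrolled. The SAP does not mention masking or masked scoring.

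**The concern.** The primary endpoint is an exercise that an interviewer administers by telephone. How far the interviewer prompts, clarifies or accepts a corrected answer can shift with what he or she expects of the patient. If expectation follows arm, the difference between arms mixes the effect of the intervention with the conduct of the call. Masked re-scoring of verbatim answers could later deal with differences in scoring. It could not undo differences in prompting.

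Followed as written, the plan allows a caller who knows the arm to administer the exercise. The gap matters because each comparison targets 11.8 percentage points with 272 patients per arm, so a lean affecting a handful of patients is not negligible.

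**Working it through.** **1. Where the arm can become known**

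| Source | Reveals | Limit |
|---|---|---|
| PCP message | Either intervention arm | Only patients with a PCP in the system; under 30% of ED patients |
| Text scheduling | EMC²+SMS | That arm only |
| Text-receipt question | EMC²+SMS | Asked at the 2-4 day call and again at the 7-14 day call |
| Bottle-label review | Either intervention arm | Within the 7-14 day call; order relative to the exercise not stated |
| Prescriber | Any arm | Arm is fixed per physician; an RA who learns a physician's arm can infer it for that physician's other patients |

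The last row is an inference. The documents do not say how RAs are told the arm, but someone in the role needs it to decide whether to message a PCP or schedule texts.

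For EMC² alone, roughly 70% or more of patients would have no PCP message, if enrolled patients resemble ED patients generally, and none would have texts. In the SMS arm the texts apply to consented patients in general. Exposure is therefore wider for EMC²+SMS versus usual care.

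**2. The plan's own figure**

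Protocol 11.2 states 82% power for 11.8 points at a type I error of 2.5% and an ICC of 0.001; 11.1 gives 272 per arm and 8 per physician. The supplied text does not give the usual-care rate.

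- Design effect = 1 + 7 × 0.001 = 1.007; effective n = 272 / 1.007 = 270.1.
- With 68.7% versus 80.5% safe use, the mean is 74.6%. SE under the null = √(2 × 0.746 × 0.254 / 270.1) = 0.0375. SE under the alternative = √((0.687 × 0.313 + 0.805 × 0.195) / 270.1) = 0.0371.
- Power = Φ((0.118 − 2.241 × 0.0375) / 0.0371) ≈ 82%.

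So 82% is attainable if usual care is near 68.7%, but it cannot be confirmed. Masking changes neither the sample size nor this power.

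**3. What a lean would do (illustration only)**

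Assume no true difference, a usual-care safe-use rate of 68%, and a net lean b towards the intervention arm. Both the size and the direction of b are assumptions.

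- SE = √(2 × 0.68 × 0.32 / 272) = 0.040.
- Rejection probability = P(Z > 2.241 − b/SE) + P(Z < −2.241 − b/SE).

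| Lean b | Patients of 272 | Share of 11.8 | b/SE | False-positive rate |
|---|---|---|---|---|
| 0 | 0 | 0% | 0 | 2.5% |
| 1 point | 2.7 | 8% | 0.25 | 3.0% |
| 3 points | 8.2 | 25% | 0.75 | 6.9% |
| 5 points | 13.6 | 42% | 1.25 | 16.1% |

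**4. Sensitivity to the unknown rate**

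This repeats the calculation with n = 270.1, the intervention error rate set to the usual-care error rate minus b, pooled variance for the critical value and unpooled variance for the spread. At a usual-care error rate of 31.4%, leans of 1, 3 and 5 points give 3.0%, 7.1% and 16.9%. Over usual-care error rates of 10% to 50%, 1 point gives 2.9-3.7%, 3 points 6.3-16.1% and 5 points 14.1-48.6%. The high ends belong to the 10% error rate, where the SE is smallest.

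**The case against.** A reader might infer that a subjective outcome will be assessed unblinded by the very person who enrolled the patient, that both primary comparisons are therefore biased, and that staff already in post could mask it at no cost. The documents do not support that reading.

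- **Subjective.** The exercise has been used in earlier studies (8.1), and 11.1 frames the outcome as staying within a maximum dose, which is a numerical threshold. Scoring may already follow a fixed rule. The interview battery is an attachment that was not supplied.
- **Unblinded.** This follows from roles and silence, not from a statement. The documents assign tasks to a role and never say that an RA calls the patients he or she enrolled. They also do not prevent it.
- **Question order.** The exercise may already come first in the interview script, which was not supplied. One can say only that the supplied text sets no order.
- **Both comparisons.** For most EMC² patients neither RA delivery task leaves a trace, so the case is weaker for EMC² versus usual care.
- **Staffing.** The additional RAs are shift cover, not a spare assessment team.
- **Size.** No source supports a lean of 3 or 5 points, and 1 point barely moves the error rate.

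All of this stands as a limit on the claim. It does not remove the gap: no assessor masking is described, the same role holds arm-specific tasks and the primary call, and a fixed scoring rule would not control prompting.

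**Conclusion.** The point holds as a gap in the protection of the primary endpoint, worth closing but not shown to have caused bias. A 7-14 day caller could know or infer the arm before or during the dosing exercise, more plausibly in the EMC²+SMS arm. No design figure in the plan is wrong on this account.

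The size cannot be estimated from the documents. Section 3 of the working shows only that a net lean of about 8 patients in 272 would take the per-comparison error rate from 2.5% to about 7% (about 6-16% over the range of usual-care rates tried). It rests on an assumed lean, an assumed rate near 68% and no true difference. Two facts would settle how much remains: who actually calls whom, and the order of questions in the script.

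**What to change.** In protocol 9.2 and 20.2:

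1. Have the 7-14 day call made by an RA who did not enrol that patient, message the PCP, schedule the texts or make the 2-4 day call, where existing cover allows. At minimum, the RAs swap patients: one does everything up to and including the 2-4 day call, another makes the 7-14 day call. Use a call sheet without arm or prescriber.
2. Confirm in the interview script, or change it so, that the dosing exercise is completed and locked before the label and text questions. Those questions should stay, because the SAP's per-protocol set depends on bottle wording and text receipt.
3. Record tablets and times verbatim and score them by a fixed rule against the prescribed regimen, without arm. Hold the regimen as numbers, not label text, since the Take-Wait-Stop wording itself identifies the intervention arms. Record for each call whether the caller was unmasked, and when.

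The cost is call-scheduling effort and possibly a reordered script; the sample size and endpoint do not change. Masking will be partial, because patients hold the bottle, may receive texts and can volunteer either fact. The sponsor must confirm that staffing allows the split, and what order the script now uses.

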21.0 Prior Approvals

21.1 We have received funding from the Agency for Healthcare Research and Quality.

22.0 Recruitment Methods

22.1 Patients will be recruited during daytime and evening hours in the Northwestern Emergency Department after being identified by the procedures outlined above in section 3.1.

22.2 Patients will be recruited in the Emergency Department at Northwestern.

22.3 During the patient recruitment period, the RA will make frequent rounds through the ED and ask physicians to identify potentially eligible patients who will be discharged home on opioid pain relievers. The RA also will carry a pager so that physicians can notify the RA if they have an eligible patient. This method of patient identification has a well-established track record within our ED for maximizing enrollment while minimizing RA downtime. If the patient is interested in participating or learning more about the study, the RA will obtain verbal permission to ask the patient a brief series of questions to determine eligibility (see criteria below). If the patient is eligible for the study, the RA will proceed with obtaining written informed consent.

22.4 The RA will explain the study to the patient. There are no advertisements.

22.5 Patients will receive a \$5 gift card at the time of enrollment, \$10 gift card will be mailed after completion of the 2-4 day phone call and

EHR-Based Medication Complete Communication (EMC²) Strategy to Promote Safe Opioid Use: A Physician Randomized Trial

they will then receive a \$20 gift card upon completion of the 7-14 day phone interview.

23.0 Local Number of Subjects

N/A

24.0 Confidentiality

24.1 Patients. After identifying eligible subjects, a member of the research staff will approach the patient and obtain written informed consent. Written consent will consist of permission to be contacted for the future phone interviews, permission for possible receiving additional information about their medication, and permission for medical record review. The research assistant will review the consent with participants. He/she will provide participants with information on the study plan and their rights as research participants. Participants' consent will be documented by their signatures. Subjects will be provided with a copy of the consent. They may withdraw at any time during the study without penalty or loss of any healthcare benefit or service to which they are entitled.

Patients who state that they do not want to receive further communication via SMS text-messaging will have the opportunity to cancel the text messages and not receive further outreach; they will be included in outcome assessments.

Data from the Illinois Prescription Monitoring Database will be obtained via individual patient record query for the enrolled patients. No protected health information will not be sent outside of Northwestern or to the State for a database query.

Patients will be assigned a unique identification number; The research database will be password protected and accessible only to the research team. Information linking subjects with their unique identifier will be kept on a separate password-protected desktop computer in a locked office within the Department of Emergency Medicine. We believe that in using these methods we will be compliant with the "Standards for Privacy of Individual Identifiable Health Information" under the Health Insurance Portability and Accountability Act of 1996 (HIPAA) Privacy Rule.

ED physicians, mid-level providers and follow-up providers

All participants will be told that their participation is voluntary; they can stop at any time, and whether they participated or not will not be disclosed to their superiors.

